The OPRC program is comprised of representatives from the NICHD (Bethesda, MD) and three Clinical Sites: Northwestern University (Chicago, IL), University of Texas Medical Branch (Galveston, TX) and Magee-Womens Hospital (Pittsburgh, PA). Two other sites, The University of Texas at Houston and the University of Utah, were added as additional sites; however, each site is conducting the study under separate INDs. The research is overseen by an internal Steering Committee, an external Data Monitoring Committee (DMC), the local Institutional Review Boards (IRBs) of each clinical site and the FDA. Details regarding the composition and responsibilities of the Steering Committee and OPRC locations are provided in the Network Policy Manual. Details regarding the composition and responsibilities of the DMC are provided in its charter.

C.2. Primary and Secondary Objectives

We will recruit 300 pregnant women with one or more prior preterm births. **Recruitment will occur at the three OPRC clinical sites and the two additional sites.** Ideally, each center will enroll approximately 100 subjects; however, enrollment may differ substantially between centers. Enrolled subjects will be randomized in a 2:1 ratio to receive a single weekly injection of 500 mg or 250 mg 17-OHPC. The 500 mg dose can be administered either as a single 2 ml weekly injection (500 mg) or two 1 ml (250 mg) weekly injections administered at the same time. Those assigned to the 250 mg weekly dose will receive 1 ml of 250 mg of 17-OHPC.

The Primary Objective of this study is to determine whether the rate of preterm birth is related to the plasma concentration of 17-OHPC.

Secondary Research Questions include the following:

1. What is the impact of race or BMI on plasma 17-OHPC concentrations?
2. Are maternal side effects increased at higher doses or higher plasma concentrations of 17-OHPC?
3. Is there an increase in adverse fetal effects from a higher dose or higher concentrations of 17-OHPC?
4. What is the relationship between dose of 17-OHPC and plasma concentrations?

5. Do single nucleotide polymorphisms in the maternal progesterone receptor, P-glycoprotein affect efficacy or the placental transfer of 17-OHPC?
6. Is efficacy of 17-OHPC affected by the gestational age at therapy initiation, the number of prior PTBs or the gestational age at delivery of prior PTBs?
7. What is the relationship between cord blood concentrations of 17-OHPC and maternal plasma concentrations?

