Patients who are greater than 21 6/7 weeks GA when they elect to withdraw from the study may not be eligible for insurance coverage of the standard 250 mg weekly dose administered by their healthcare provider. In this case, the study will continue to provide the standard 250 mg weekly dose until 36 6/7 weeks gestation or until delivery.

If a subject in the ancillary cohort withdraws from the study, her treatment will continue to be managed by her healthcare provider. Any data collected will be retained and used as appropriate.

C.8. Study Halting Criteria

We have established study halting criteria since the 500 mg dose is not FDA approved. We will use subjects in the 250 mg RCT group as a comparator for adverse effects and to establish criteria for stopping the study. We will not use subjects in the ancillary study who are receiving the 250 mg dose as a comparator since they will not have been randomized.

The DMC will review enrollment and AEs on a regular basis (every 4 months). Enrollment will not stop unless the Network is directed to stop by the DMC or the FDA. Criteria that warrant discussion of halting the study by the DMC will include more than expected occurrence of the SAEs previously known to be associated with 17-OHPC use, or SAEs unexplained by the patient's medical condition. Preterm birth is an expected pregnancy complication in this group of subjects and is associated with significant and serious fetal and neonatal morbidities and mortality mostly related to severe prematurity. Therefore, when the DMC evaluates SAEs, a distinction will be made as to whether the SAE is thought to be related to the patient's medical

or pregnancy condition (e.g. severe preeclampsia, extreme prematurity, etc) or whether it is thought to be related to study medication. Study halting criteria include:

1. Fetal and neonatal deaths.

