A safety signal for an excessive number of early pregnancy losses and stillbirths was identified in the Meis study by the FDA in their review of the Makena NDA. The rate of loss was 3.6 in the 17-OHPC group and 1.3 % in the control group. If this signal is related to plasma concentrations of 17-OHPC, then a greater number of these adverse outcomes might be seen. Fetal and neonatal deaths will be evaluated on an ongoing basis. Study coordinators will report serious adverse events to the site PI, the LCC, and the study Lead PI within 24 hours of notification. Information not available at the time of the initial report should be submitted as a follow-up report within 48 hours of notification. It would appear reasonable to set some criteria to alert the Medical Monitor and the DMC that a review is necessary. We have set this alert at a rate of pregnancy loss (20 0/7 weeks till delivery) or stillbirth of 1.5 times higher in the 500 mg weekly group than in the 250 mg group. The DMC should review all deaths to determine the relationship to study drug and to determine what if any action is needed. Enrollment in the study will continue during this review. After the review the DMC, in conjunction with NICHD and the Medical Monitor, will determine whether the study should be stopped or continued.

2. Thromboembolic Events (deep vein thrombosis or pulmonary embolus)

There is a potential risk of thrombosis from progestin treatment but this risk is low. Genetic predisposition to clotting is seen in over 5% of the population and pregnancy increases the risk of thrombosis so clotting during pregnancy is uncommon but NOT an unexpected event. Doses of 17-OHPC of 250 mg weekly have not been associated with an increased risk of clotting but the potential exists that higher doses of 17-OHPC may increase the risk of thrombosis. We would expect no more than 3 cases of thrombosis (3%) in the 150 subjects recruited to the 250 mg weekly group. If the number of cases of deep vein thrombosis or pulmonary embolus in the 500 mg weekly group exceeds the number of cases in the 250 mg group by more than 3% (3 cases) then these cases will be identified by the Medical Monitor and reviewed by the DMC for 17-OHPC causality. All SAEs are reported promptly to the site PIs, Medical Monitor and study lead and are reviewed by the DMC. The DMC should review all the thrombotic events to determine the relationship to study drug and to determine what if any action is needed.

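### The between-arm alert under the fetal and neonatal deaths criterion leaves out neonatal deaths and has no rule for zero events on 250 mg

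*Combined protocol and SAP*

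**What the plan says.** Section C.8 (Study Halting Criteria) heads its first item "1. Fetal and neonatal deaths" and adds: "Fetal and neonatal deaths will be evaluated on an ongoing basis". The background signal is one of early pregnancy losses and stillbirths: "The rate of loss was 3.6 in the 17-OHPC group and 1.3 % in the control group". The one comparison between randomized arms, 500 mg against 250 mg, is then defined: "We have set this alert at a rate of pregnancy loss (20 0/7 weeks till delivery) or stillbirth of 1.5 times higher".

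The same section provides that:
- the alert brings the Medical Monitor and the DMC to a review, and enrollment continues meanwhile;
- the DMC should review all deaths for relation to study drug;
- serious adverse events are reported within 24 hours;
- the DMC looks at adverse events every 4 months.

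It gives no rule for zero events on 250 mg, no minimum count and no statement of when the ratio is calculated.

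**The concern.** The item names two outcomes and the trigger counts one. Its window closes at delivery. On a plain reading, a stillborn infant at 22 weeks counts and a liveborn infant of the same gestation who dies does not.

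This matters in this population because C.8 itself says that neonatal mortality here comes mostly from severe prematurity, and asks the DMC to separate such deaths from drug-related ones. Judged singly, each newborn death can be put down to prematurity. An excess on 500 mg would show in a comparison of arms, and for newborn deaths no such comparison is specified.

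The second gap is the zero denominator. With no losses on 250 mg, the plan does not say whether the first loss on 500 mg meets the ratio. The alert's behavior depends heavily on the answer.

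**Working it through.** **What can trip the alert.** Let x and y be the counted events on 500 mg and 250 mg. The alert fires if x/n500 ≥ 1.5 × y/n250. Neonatal deaths enter neither x nor y, so ten newborn deaths against none leave the ratio unchanged. This part needs no assumption about rates.

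**Inputs for the ratio.**
- Arm sizes: "We will recruit 300 pregnant women with one or more prior preterm births" (C.2), and "Enrolled subjects will be randomized in a 2:1 ratio to receive a single weekly injection of 500 mg or 250 mg 17-OHPC". So n500 = 300 × 2/3 = 200 and n250 = 100.
- Loss rates: 1.3% and 3.6% are the only ones given (C.8). The plan does not state the rate it expects in this trial; 2.0% is added as an intermediate assumption.
- Number of reviews: D.2 gives a pool above 300 a year and acceptance of 30% to 50%. That is 90 to 150 women a year, hence 300/90 ≈ 3.3 years (10 four-monthly reviews) to 300/150 = 2 years (6 reviews). Nine reviews correspond to 36 months.
- Simplification: enrollment is even and outcomes are counted with enrollment.

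The plan states no operating characteristic for this alert, so there is no figure to reproduce.

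**Single final look, exact.** With 200 versus 100, the condition is x ≥ 3y with x ≥ 1. Summing Bin(x; 200, p) × Bin(y; 100, p) over that region gives 0.433, 0.399 and 0.324 at p = 1.3%, 2.0% and 3.6%.

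**Repeated looks, simulated.** The same rule was applied to cumulative counts at each equally spaced review. The entries are the percentage of trials in which the alert fires at least once.

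| True 250 mg rate | Equal rates, 6 / 9 / 10 reviews, 1 vs 0 counts | Equal rates, 9 reviews, 250 mg loss required | Equal rates, one final look | True doubling, 9 reviews, 1 vs 0 counts |
|---|---|---|---|---|
| 1.3% | 65 / 67 / 68 | 24 | 43 | 87 |
| 2.0% | 67 / 70 / 71 | 39 | 40 | 90 |
| 3.6% | 65 / 70 / 72 | 53 | 32 | 92 |

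The zero rule matters because, with equal rates, the first loss falls on 500 mg with probability 200/300 = 2/3, and 1 versus 0 exceeds any ratio.

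**Sensitivity.**
- A strict inequality (more than 1.5 times) gives 63–68% over 6–10 reviews with 1 versus 0 counted, and 26–35% at one final look.
- Reading the threshold as 2.5 times the 250 mg rate gives 53–63% over 6–10 reviews.
- C.8 item 2 says "We would expect no more than 3 cases of thrombosis (3%) in the 150 subjects recruited to the 250 mg weekly group", which conflicts with 2:1 allocation of 300 and must be reconciled. With 150 versus 150 the result is 56–64% over 6–10 reviews.

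**What an exact probability would add.** Given D deaths in all and equal rates, the number on 500 mg is approximately Bin(D, 2/3).
- 1 versus 0 has probability 2/3 = 0.67.
- 3 versus 0 has probability (2/3)³ = 0.30.
- 3 or more of 4 has probability 4 × (2/3)³ × (1/3) + (2/3)⁴ = 48/81 = 0.59, although 3 versus 1 meets the 1.5 threshold exactly.

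**A minimum of 5 losses in total (9 reviews, 1 vs 0 otherwise counted).** False alerts fall to about 16%, 33% and 50% at the three rates. Detection of a doubling falls from 87% to about 60%, from 90% to 79%, and from 92% to 88%.

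**The case against.** The strongest reply is that little turns on the trigger. Its only effect is a review, and deaths are reviewed in any case: the DMC should examine all of them, reporting is fast, and an unexpected frequency of known serious events separately warrants discussion of halting. A reader might infer from the omission that newborn deaths go unmonitored. The documents do not support that.

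The narrower count also has a stated basis, since the cited signal concerns pregnancy losses and stillbirths. Pooling prematurity-related newborn deaths into one ratio could dilute it. That stands, and is why separate as well as combined counts are needed.

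A sensitive alert is a legitimate choice for a dose that is not FDA approved, when a false alert costs a review and not a pause. That stands too. The DMC charter, which is not among these documents, may contain further rules.

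What remains is that, with every death reviewed anyway, the alert's added value is the comparison of arms. For one of the two outcomes in its heading it makes none.

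**Conclusion.** The concern holds for the numerical trigger and not for death monitoring as a whole. The omission of neonatal deaths follows from the text alone. The false-alert figures rest on 200 versus 100 women, true loss rates of 1.3–3.6%, and a choice the plan leaves open: about 65–72% over 6–10 reviews if 1 versus 0 counts, about 24–53% over 9 reviews if a 250 mg loss is required, and about 32–43% at one final look.

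Two stronger readings are tempting and not supported. One is that about 70% of trials with no difference will raise an alert: that needs both repeated calculation and 1 versus 0 as a trigger, and the plan states neither for this alert. The other is that the alert cannot tell harm from no harm: at 3.6% over 9 reviews it fires in 70% without a difference and 92% with a doubling. That is weak discrimination, but it is not none.

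**What to change.** In C.8 item 1, and in the DMC charter if needed:
1. Include neonatal deaths in the alert, and show fetal and neonatal deaths by arm both separately and combined, so that the loss and stillbirth signal is not diluted.
2. State how the ratio is handled when there are no events on 250 mg, and when it is calculated. A rule that ignores 1 versus 0 also lowers detection, so it should be chosen knowingly.
3. Give the DMC, with every alert, the exact binomial probability of the observed split under 2:1 allocation.
4. Keep the individual review of every death.

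Do not impose a minimum of 5 deaths. Given the loss of detection shown above, largest at the lowest base rate, any minimum is for the sponsor and DMC to choose with those figures in view. They were computed for losses only; adding neonatal deaths would raise the counts.

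The cost is a few sentences and slightly more DMC reporting. Prematurity-related newborn deaths may also raise the number of alerts that need review.

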8. Does the 17-OHPC concentration in maternal plasma or whole blood correlate better with certain pharmacological and clinical outcomes?

Subjects in the ancillary cohort will already be receiving 250 mg 17-OHPC weekly as part of their standard of care, based on their clinical history. The *primary objective* in the ancillary cohort is identical to the RCT.

The secondary research questions are similar to the RCT except for numbers 2, 3, and 7 above. Data will be collected from subjects in the ancillary cohort, but will not be utilized for secondary research questions 2 and 3 above. These research questions cannot be adequately addressed because subjects in the ancillary cohort are not randomized. Research questions 5 (cord blood only) and 7 cannot be addressed because biological fluids will not be collected at delivery in the ancillary cohort.

C.3. Screening Procedures

All patients who present for prenatal care before 20 6/7 weeks are eligible for screening. The latest gestational age to start treatment in the RCT is 21 6/7 weeks. Subjects who either refuse the RCT or are not approached may be eligible for participation in the ancillary cohort. The inclusion/exclusion criteria will be reviewed with the patient's chart. Potentially eligible subjects will be told about the study and asked to sign a medical records release so that the medical records of her previous deliveries may be obtained. Documentation of the previous deliveries will be reviewed to ensure the patient meets the inclusion criteria. If a patient appears to meet the criteria for enrollment and expresses interest in the study, she will be told about the study and asked to sign the informed consent form. A copy of the consent form will be provided to the patient.

C.3.i. Eligibility Criteria

a. RCT Eligibility Criteria

Inclusion Criteria - Subjects in the RCT must meet all of the following:

1. Pregnant female with documented prior birth between 16 0/7- 35 6/7 week gestation from spontaneous preterm labor or preterm premature rupture of membranes
2. Gestational age (GA) < 22 weeks, based on study determined GA (as treatment must start between 16 0/7 and 21 6/7 weeks)
3. Singleton gestation
4. Age between 18 – 45 years
5. Able to give informed consent and undergo study procedures

Exclusion Criteria - Subjects in the RCT must not meet any of the following:

1. Plan for cerclage
2. Plan for progesterone treatment other than study medication

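### C.8's thrombosis alert compares raw case counts and assumes 150 women at 250 mg although allocation is 2:1; its only loss alert starts at 20 0/7 weeks and excludes neonatal deaths

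*Combined protocol and SAP*

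**What the plan says.** C.8 gives halting criteria because the 500 mg dose is unapproved, and it names the comparator: "We will use subjects in the 250 mg RCT group as a comparator for adverse effects". The ancillary cohort is excluded from that comparison. On allocation, C.2 says "Enrolled subjects will be randomized in a 2:1 ratio", with 300 women to be recruited.

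Item 1 is headed as covering fetal and neonatal deaths. Its rationale is an FDA finding in an earlier placebo-controlled trial of the drug: "A safety signal for an excessive number of early pregnancy losses and stillbirths was identified", at 3.6% against 1.3%. The numeric trigger is "We have set this alert at a rate of pregnancy loss (20 0/7 weeks till delivery) or stillbirth of 1.5 times higher", comparing 500 mg with 250 mg. Beyond the trigger, "Fetal and neonatal deaths will be evaluated on an ongoing basis", and the DMC is asked to review every death. On timing, RCT inclusion criterion 2 (C.3.i) says "treatment must start between 16 0/7 and 21 6/7 weeks".

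Item 2 states the expectation "We would expect no more than 3 cases of thrombosis (3%) in the 150 subjects recruited to the 250 mg weekly group". Its alert applies when the number of thrombotic cases in the 500 mg group "exceeds the number of cases in the 250 mg group by more than 3% (3 cases").

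**The concern.** A between-arm alert should respond to a difference in risk between the arms, for the events that motivated it.

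The thrombosis alert is worded in numbers of cases. With twice as many women at 500 mg, that arm should have about twice the cases when the dose makes no difference. The 150 is what equal allocation of 300 would give, so the rule appears not to match the 2:1 design. An alert under it does not by itself tell the DMC that risk is higher at 500 mg.

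The loss alert is a ratio of rates, so 2:1 allocation does not distort it. Its problem is which events it counts. The cited signal includes early losses and treatment can start at 16 0/7 weeks, yet counting begins at 20 0/7. Neonatal deaths appear in the item's heading but in no numeric rule. An excess of either at 500 mg would leave the only numeric death alert in C.8 unmoved.

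**Working it through.** **Inputs from the plan.** 300 women at 2:1 (C.2): 300 × 2/3 = 200 at 500 mg and 300 × 1/3 = 100 at 250 mg. Thrombosis: 3 cases, 3%, 150 women (C.8 item 2). Loss: 3.6%, 1.3% and the 1.5-fold trigger (C.8 item 1).

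**Assumed.** The true thrombosis risks, the share of losses before 20 0/7 weeks, the size of any dose effect and the neonatal death rates. The plan gives none of these, apart from 3% as an upper expectation for thrombosis.

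**Step 1: the plan's own figure.** 3/150 = 2.0%, and 3% of 150 is 4.5 cases. 3/100 = 3.0%. So 3 cases equal 3% only with 100 women, the size of the 250 mg arm under 2:1. In the 500 mg arm, 3% is 6 cases.

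**Step 2: the gap due to allocation alone.** At equal risk p the expected difference in counts is 200p − 100p = 100p, which is 1, 2 or 3 cases at 1%, 2% or 3%. At 3% it uses up the whole margin. With 8/200 and 4/100 both rates are 4%, yet the excess is 4 cases and the alert fires.

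**Step 3: how often the thrombosis alert fires.** Take independent X500 ~ Bin(200, p500) and X250 ~ Bin(100, p250) at one look with full enrolment. P(alert) is the sum of the joint probabilities over all pairs with X500 − X250 > 3. A proportion rule at 1.5 points is X500/200 − X250/100 > 0.015, which is X500 − 2·X250 > 3, the same 3-case margin scaled to 2:1.

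| True risk, 500 mg vs 250 mg | Count rule, 200 vs 100 | Count rule, 150 vs 150 | >1.5 points, 200 vs 100 | >3 points, 200 vs 100 |
|---|---|---|---|---|
| 1% vs 1% | 7% | 2% | 6% | 0.2% |
| 2% vs 2% | 26% | 7% | 15% | 2% |
| 3% vs 3% | 42% | 12% | 20% | 5% |
| 4% vs 2% | 79% | – | 56% | 26% |
| 6% vs 2% | 97% | – | 85% | 64% |

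With 3 cases at 250 mg, the count rule fires from 7/200 (3.5%), the 1.5-point rule from 10/200 (5.0%) and the 3-point rule from 13/200 (6.5%). Repeated 4-monthly looks would raise the chance of at least one alert.

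**Step 4: what the loss alert can see.** It fires when X500/200 ≥ 1.5 × X250/100 with at least one 500 mg event. At equal rates it fires 43% of the time at 1.3% and 32% at 3.6%, so it is already noisy. Now take a total loss rate of 3.6% at 250 mg with 25%, 50% or 75% of losses before 20 0/7 weeks. The current alert counts only the rest (2.7%, 1.8%, 0.9%) and fires 36%, 41% or 44% of the time, whatever 500 mg does to early losses.

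**Step 5: one composite or separate alerts.** If 500 mg tripled early losses only, a single alert counting every loss from first dose would fire 55%, 74% or 87% of the time (44%, 55% or 65% if they doubled). The composite costs power elsewhere. If only losses after 20 0/7 weeks doubled, the current alert fires 72%, 70% or 68%, but the composite 65%, 55% or 44%. Adding neonatal deaths dilutes further: a doubled 3.6% loss rate fires 74%, falling to 62% or 56% once 2% or 3% of neonatal deaths unaffected by dose are added.

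A separate alert on early losses (0.9%, 1.8%, 2.7% at 250 mg), by the same enumeration, fires 82%, 87% or 91% if they triple and 44%, 41% or 36% with no effect. With no effect, the chance of at least one of the early and late alerts, treated as independent, is 1 − (1 − 0.36)(1 − 0.44) = 0.64 at a 25% share. It is 1 − 0.59² = 0.65 at 50%, and 0.64 again at 75%.

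**The case against.** The strongest reply is that nothing escapes review. C.8 has the DMC review all deaths, all thrombotic events and all SAEs, with AE review every 4 months and a general criterion for more events than expected. The Medical Monitor also follows SAEs continuously (C.9). That stands. A reader might infer that early losses and neonatal deaths go unmonitored, and the documents do not support that. What is missing is a numeric between-arm trigger. Case review asks whether each event is drug-related, and C.8 tells the DMC to separate events attributable to the pregnancy, such as extreme prematurity. A comparison with the randomised arm does not depend on that attribution.

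Second, over-alerting on thrombosis is cautious. That also stands: the count rule is the more sensitive one, and its cost is an extra look at cases the DMC sees anyway. The 26% and 42% sit towards the plan's upper expectation, and women with past thrombosis are excluded. At an equal 0.5% (assumed) the count rule fires 1.2% of the time and the 1.5-point rule 1.1%, so the distortion almost disappears.

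Third, the 3% might be meant as a difference in rates. On that reading chance alerts are 2% to 5% at an equal 2% to 3% risk. But the sentence compares numbers of cases and equates 3% with 3 cases, which cannot hold in both arms. The wording needs correcting on either reading.

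Fourth, the early-loss figures rest on assumed shares and effects. Some women start as late as 21 6/7 weeks and have no treated time before 20 0/7, which makes a high early share less plausible. The gap in the definition does not depend on those figures; its size does.

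**Conclusion.** Item 2 is wrong as written. The 150 contradicts 2:1 allocation of 300, and the case-count rule can fire with no difference in rates: 7%, 26% or 42% of the time at an equal 1%, 2% or 3% risk. These figures assume full enrolment at 200 vs 100, independent binomials and one look. A reader might conclude that the rule hides harm. It does the opposite, since the error runs towards extra alerts.

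Item 1 has a gap in what it counts. Losses between first dose and 19 6/7 weeks and neonatal deaths have no arm-level alert, although the cited signal covers early losses and the heading covers neonatal deaths. The size of the consequence is uncertain because the plan gives no early-loss share, dose effect or neonatal death rate.

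The alerts prompt review and do not stop the trial. They are the only numeric triggers in C.8. Whether others exist cannot be judged, because the DMC charter and the safety monitoring plan are not among these documents.

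**What to change.** **Item 2.** Correct 150 to about 100. State the alert as a difference in proportions per woman randomised, and choose the threshold deliberately. More than 1.5 percentage points is the 3-case rule scaled to 2:1. The price is sensitivity: at 4% vs 2% it fires 56% of the time against 79% for the count rule, and a 3-point threshold only 26%. If the higher sensitivity is wanted for an unapproved dose, set a lower threshold openly.

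**Item 1.** Keep the existing alert from 20 0/7 weeks. Add two separate 1.5-fold by-arm alerts per woman randomised, one for losses from first dose to 19 6/7 weeks and one for neonatal deaths. Do not merge them into one composite, which would dilute a late-loss signal.

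**Reporting.** At the existing 4-monthly DMC review, show these events by arm regardless of attributed cause, with ratio and 95% CI, beside the case-level causality review. How to weigh the two stays with the DMC. If the charter or safety monitoring plan already does this, cite it in C.8.

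**Cost.** Edits to two items and one table, using data already collected. Chance alerts will be more frequent: about 64% to 65% for at least one of the two loss alerts with no effect at one look, against 36% to 44% for the current alert alone, and more once the neonatal alert is added. Intervals will be wide. For example, 14/200 vs 4/100 is a ratio of 0.07/0.04 = 1.75, with log-scale SE √(1/14 − 1/200 + 1/4 − 1/100) = 0.55 and 95% CI 0.59 to 5.18.

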C.9. Medical monitor and Logistic Coordinating Core

A Medical Monitor has been selected for this trial. The Medical Monitor will receive reports from each clinical center which will be compiled by the NICHD funded **Logistic Coordinating Core (LCC)**. The LCC facilitates and coordinates the OPRC clinical study activities and ensures that all activities are implemented.

The role of the Medical Monitor will include:

- Ongoing monitoring of SAE reports submitted by the clinical centers to identify safety concerns and suggest protocol modifications, if necessary
- Advise IND sponsor, Principal Investigator(s), and DMC regarding SAEs and safety concerns
- Provide reports when necessary to the Principal Investigator and DMC

D. Statistical Analysis and Sample Size Justification

D.1. Primary and Secondary Outcomes

The primary outcome is the rate of preterm birth (delivery prior to 37 0/7 weeks) according to 17-OHPC concentration.

Secondary outcomes include:

- The rate of spontaneous PTB prior to 32 0/7 and 35 0/7 weeks according to the concentration of 17-OHPC.
- The impact of dose, race, BMI and co-medications on plasma 17-OHPC concentrations
- Plasma concentrations of 17-OHPC, mono-hydroxylated metabolite of 17-OHPC
- Concentrations of progesterone and 17-hydroxyprogesterone in maternal and cord blood according to the weekly dose of 17-OHPC
- The frequency of maternal side effects according to dose and plasma concentration
- The frequency of neonatal complications according to dose and plasma concentration
- Impact of dose on rates of spontaneous PTB
- The correlation of progesterone and 17-hydroxyprogesterone in maternal plasma and whole blood to pharmacological and clinical outcomes

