The primary outcome will be the rate of preterm birth (<37 weeks) according to the plasma concentration of 17-OHPC (as a continuous variable) from the 26-30 week sample. The distribution of plasma concentration is expected to be highly positively skewed; thus, a natural logarithmic transformation will be applied to plasma concentrations to produce normally distributed values. A Cox proportional hazard model will be employed to analyze the effect of continuous log-transformed plasma concentration on event-free survival (in this case, “event-free survival” meaning “not birthed until term”). Specifically, the hazard of delivering preterm will be modeled as a function of log-transformed plasma concentration and additional covariates that may influence treatment effectiveness (e.g., BMI, race, gestational age at study entry). Adjusted survival curves will be calculated using the relationship between the hazard function and the survival function. A Wald test will be performed to determine whether the hazard ratio corresponding to a one-unit increase in log-transformed plasma concentration is significantly different from zero. Wald and likelihood ratio tests will also be employed to test for the significance of additional covariates, and stratified analyses may be considered if appropriate (i.e., race-specific analyses). This semi-parametric modeling approach will allow us to analyze the effect of, and not just the presence of, covariates on event-free survival in a robust manner.

Secondary outcomes that are also survival outcomes (such as spontaneous PTB, spontaneous PTB before 32 weeks and before 35 weeks, and indicated PTB) will be analyzed in a similar fashion to the primary outcome analysis described above. For other secondary outcome measures that are continuous variables (maternal and infant hospital days, maternal and fetal plasma concentrations of progesterone, hydroxyprogesterone, 17-OHPC and its metabolite, etc.), linear regression models with appropriate covariates will be utilized.

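### Research question 3 asks about fetal harm from the higher dose, but Section D plans no analysis of fetal or neonatal death, and the C.8 monitoring alert does not fill that gap

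*Combined protocol and SAP*

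**What the plan says.** All references are to the combined protocol and SAP.

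- **The question.** C.2, research question 3: "Is there an increase in adverse fetal effects from a higher dose or higher concentrations of 17-OHPC". C.2 also keeps the ancillary cohort out of this question because it is not randomised, so the plan itself treats it as a randomised comparison.
- **The known signal.** C.8 item 1 cites an earlier excess of pregnancy losses and stillbirths: "The rate of loss was 3.6 in the 17-OHPC group and 1.3 % in the control group". It adds that more such outcomes could occur if the signal depends on concentration.
- **The planned outcomes.** The only offspring-harm entry in the D.1 list is "The frequency of neonatal complications according to dose and plasma concentration". The analysis text in D.1 adds linear regression for continuous measures, among them "maternal and infant hospital days". It gives no components, no denominator, and no rule for a stillbirth or neonatal death.
- **The monitoring.** C.8 item 1 states: "Fetal and neonatal deaths will be evaluated on an ongoing basis". The alert threshold is "pregnancy loss (20 0/7 weeks till delivery) or stillbirth of 1.5 times higher in the 500 mg weekly group than in the 250 mg group", and every death also goes to DMC review.

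**The concern.** The outcome that the plan itself identifies as the fetal safety signal has no place in the planned final analysis. A stillborn fetus has neither a neonatal complication nor an infant hospital stay. If the two listed measures are taken in live births, the dose comparison is conditioned on a post-randomisation event that the drug is suspected of affecting. Extra fetal deaths at 500 mg would then be invisible. If the lost fetuses were the frailer ones, the remaining live births would look healthier.

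Hospital days have a second problem. In a regression on raw days, an infant who dies soon after birth contributes a short stay, which reads as a good result.

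At stake is the fetal-safety answer for a dose that C.8 says is not FDA approved.

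**Working it through.** **No figure to reproduce.** The plan gives no sample size, power or event count for question 3. D.2 offers only a general assurance that the sample suffices for secondary outcomes. What follows is an illustration with declared assumptions.

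**Inputs from the plan.** 300 women randomised 2:1 (C.2) gives about 100 at 250 mg and 200 at 500 mg. (C.8 item 2 mentions 150 women at 250 mg, which does not fit that ratio and is not used.) Earlier loss rates are 3.6% and 1.3%; the alert ratio is 1.5 (C.8 item 1).

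**Assumptions.** Loss is 3.6% at 250 mg. At 500 mg it is either 3.6 × 1.5 = 5.4% or 3.6 × (3.6/1.3) = 10.0%. Complications affect 20% of live births at 250 mg. The extra losses at 500 mg would otherwise have had complication risk q, taken as 20%, 50% or 100%.

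**Formulas at 500 mg.**
- Extra losses E = 200 × (loss at 500 mg − 0.036)
- Live births = 192.8 − E
- Complicated live births = 0.20 × 192.8 − qE = 38.56 − qE
- Live-birth rate = (38.56 − qE)/(192.8 − E)
- Composite in all women = (38.56 − qE + losses)/200

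At 250 mg there are 96.4 live births, of which 19.28 are complicated. The live-birth rate is 20.0% and the composite is (19.28 + 3.6)/100 = 22.9%.

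Worked case, 5.4% and q = 50%: E = 3.6; live-birth rate = 36.76/189.2 = 19.4%; composite = (36.76 + 10.8)/200 = 23.8%.

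| Loss at 500 mg | q | Live-birth rate, 250 vs 500 | Composite, 250 vs 500 |
|---|---|---|---|
| 5.4% | 20% | 20.0% vs 20.0% | 22.9% vs 24.3% |
| 5.4% | 50% | 20.0% vs 19.4% | 22.9% vs 23.8% |
| 5.4% | 100% | 20.0% vs 18.5% | 22.9% vs 22.9% |
| 10.0% | 20% | 20.0% vs 20.0% | 22.9% vs 28.0% |
| 10.0% | 50% | 20.0% vs 17.9% | 22.9% vs 26.1% |
| 10.0% | 100% | 20.0% vs 14.3% | 22.9% vs 22.9% |

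The live-birth rate never shows the harm. The composite shows it unless every lost fetus would have had a complication, in which case the composite is exactly equal. It therefore cannot be the only answer.

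**Against sampling error.** With about 96 and 189 live births at 20%, SE = √[0.16 × (1/96 + 1/189)] = 5.0 points. The shifts at q = 50% (0.6 and 2.1 points) are well under one SE.

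**Hospital days.** If d extra early neonatal deaths per 100 live births each remove L days, the mean falls by dL/100. The plan gives neither value. Assuming d = 1 to 2 and L = 30 to 60, the fall is 0.3 to 1.2 days.

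**What a direct comparison of loss can deliver.** Power = Φ[(difference − 1.96 × SE₀)/SE₁], with SE₀ pooled and SE₁ unpooled.
- 3.6% vs 5.4%: (0.018 − 1.96 × 0.0262)/0.0245 = −1.36, power about 9%
- 3.6% vs 10.0%: power about 49%

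The 95% interval around an observed 1.8-point difference would be 1.8 ± 1.96 × 2.45, or −3.0 to 6.6 points.

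**What the C.8 alert delivers.** Apply it once at full enrolment, firing when the 500 mg rate is at least 1.5 times the 250 mg rate with at least one loss at 500 mg. Exact binomial sums give a firing probability of 0.32 with no true difference (3.6% in both arms), 0.55 at a true ratio of 1.5 and 0.91 at 2.77. It works as a prompt for review, not as an estimate. Its loss window also opens at 20 0/7 weeks, although treatment can start at 16 0/7 (C.5).

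**The case against.** The strongest reply is that C.8 already covers deaths. It makes fetal and neonatal deaths the first halting criterion, takes the randomised 250 mg arm as comparator, compares loss and stillbirth by dose, and sends every death to the DMC. Pregnancy and neonatal outcomes are also collected at delivery (C.6.iv). This stands. A reader might infer that fetal deaths disappear from the trial; the documents do not support that. They are monitored but absent from the planned final analysis.

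Three other stronger readings also fail.

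- **That the plan prescribes a live-birth denominator.** It states none; live births is the natural reading of an undefined measure. The D.1 list is also worded as non-exhaustive, and adverse-event detail is deferred to a safety monitoring plan not available here.
- **That early neonatal deaths also flatter the complication rate.** An infant who dies after birth stays in a live-birth denominator, and nothing says the death would not count as a complication. Only hospital days are exposed in that way.
- **That the bias is certain or large.** With average-risk losses there is no favourable shift at all, and in most of the scenarios above the shift is a fraction of the standard error.

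It can also be said that the preterm-birth analyses state no live-birth restriction, so a preterm stillbirth would count as an event. That is true, but it mixes stillbirths with live preterm births and does not answer question 3.

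**Conclusion.** The concern holds as a gap in the planned analysis. Section D answers a question about fetal harm with measures that, on their natural reading, need a live birth, and it gives no rule for deaths. The C.8 alert protects participants during the trial but leaves no estimate or interval for the final report.

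The direction of possible bias is neutral to favourable for a harmful dose. Its size is not known. In the illustration it runs from 0 to 2.1 points at q up to 50%, and to 5.7 points only if loss is 10.0% and every extra lost fetus would otherwise have had a complication. All of this rests on the assumed 20% complication rate, the assumed loss rates at 500 mg and the assumed q. The case for change is that the named safety outcome goes unreported, whatever the size of the bias.

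**What to change.** 1. In D.1, add as the lead answer to question 3: fetal loss, stillbirth or neonatal death by randomised dose, counted from randomisation, with all randomised women as denominator and a confidence interval. Label it descriptive, since power is about 9% to 49% in the scenarios above. State the window for ascertaining neonatal death and how a termination (C.7.i) is counted. Leading with dose also avoids a gap in any concentration analysis: the 26-30 week sample, named for the primary outcome, would not exist for earlier losses.
2. Define the components and denominator of neonatal complications. Report death or major neonatal complication in all randomised women, and the live-birth-only rate, as supportive only, because the composite can be equal when deaths replace complications.
3. Analyse infant hospital days by a rank or ordinal method with deaths ranked worst, instead of linear regression on raw days.
4. The sponsor should reconcile C.8 item 1, whose heading covers fetal and neonatal deaths while its numeric alert counts only pregnancy loss or stillbirth.

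**Cost.** Mainly wording in D.1, slightly more analysis, and wide intervals. Most of the data are already collected at delivery (C.6.iv) or through serious adverse event reporting (C.8). The exception is neonatal death: weekly contact ends at delivery (C.6.iii) and no neonatal follow-up period is stated, so complete ascertainment may need a further record check.
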